1.1 Synopsis

Protocol Title: Phase I, Open-label, Single-sequence, Cross-over Study of the Effect of Multiple Doses of Itraconazole on Single-dose Tepotinib Pharmacokinetics in Healthy Participants

Short Title: Tepotinib Drug-Drug Interaction Study With Itraconazole in Healthy Participants

CCI

Objectives and Endpoints:

Objectives	Endpoints	Ref #
Primary		
To investigate the effect of multiple doses of itraconazole on tepotinib PK in healthy participants	
Plasma tepotinib: $AUC_{0-\infty}$, $AUC_{0-t_{last}}$, and C_{max}	1
Secondary		
To assess the safety and tolerability of tepotinib when administered together with itraconazole in healthy participants	
Nature, occurrence, severity, and seriousness of TEAEsAbsolute values and changes in safety laboratory testsSingle 12-lead ECGs evaluated by InvestigatorVital signs assessed from time of first dose to end of study participation	2
To characterize the effect of multiple doses of itraconazole on additional tepotinib PK parameters in healthy participants	
Plasma tepotinib: CL/F, V_z/F, t_{max}, and $t_{1/2}$	3

ECG=electrocardiogram, PK=pharmacokinetics, TEAE=treatment emergent adverse events.

Overall Design: This will be a nonrandomized, open-label, single-sequence, cross-over Phase I study in healthy participants.

Brief Summary:

The purpose of this study is to assess the effect of multiple doses of itraconazole on single-dose tepotinib pharmacokinetics in healthy participants. Study details include:

[figure not shown]
- Study Duration: up to 48 days
- Treatment Duration: single dose of tepotinib on Days 1 and 12, 11 days of treatment with itraconazole (Days 8 to 18)
- Visit Frequency: residence in the Clinical Research Unit from Days -1 to 4 and Days 11 to 15, ambulatory daily visits from Days 5 to 10 and 16 to 20

Number of Participants: A maximum of 18 participants will be assigned to study interventions such that at least 14 evaluable participants complete the study.

Study Intervention Groups and Duration: 21 days of intervention period including Safety Follow Up on Day 20; single dose of tepotinib on Days 1 and 12, 11 days of treatment with itraconazole (Days 8 to 18).

Involvement of Special Committee(s): No

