1.2 Schema

1.3 Schedule of Activities

Assessments & Procedures	Screening	Intervention Period (Days)																			Safety Follow Up	Notes	
		-1	1	2	3	4	5	6	7	8	9	10	11	12	13	14	15	16	17	18	19		
Study Day	-28 to -2																						
Informed consent	X																						Prior to any Screening activity.
Participants resident at CRU		X	X	X	X	X							X	X	X	X	X						
Ambulatory visits at CRU							X	X	X	X	X							X	X	X	X	X	
Eligibility criteria	X	X																					Recheck of eligibility criteria on Day -1, (Sections 5.1 and 5.2).
Demography, height & weight	X																						Demography to include, at minimum, age (year of birth), sex, race, and ethnicity.
Medical history	X																						
Physical examination	X	X										X								X			Brief examination on Day -1 to check eligibility. Section 8.2.1.
Serum pregnancy test	X	X																			X		Section 8.3.4 and Appendix 5.
FSH	X																						In postmenopausal women, only (Appendix 5).
Viral serology, TSH	X																						Appendix 5.
Clinical laboratory tests (blood and urine)	X	X										X		X	X	X	X				X		Details in Appendix 5.
Cotinine, drug screen, alcohol breath test, SARS-CoV-2	X	X											X										Details in Appendix 5.
Vital signs & safety ECG	X	X	X	X									X	X	X	X	X				X		Predose on dosing days. Sections 8.2.2 and 8.2.3.

Assessments & Procedures	Screening	Intervention Period (Days)																				Safety Follow Up	Notes
		-28 to -2	-1	1	2	3	4	5	6	7	8	9	10	11	12	13	14	15	16	17	18	19	
Study Day	-28 to -2																						
AE/concomitant medication review	X	X	X	X	X	X	X	X	X	X	X	X	X	X	X	X	X	X	X	X	X	X	Section 6.8. Section 8.3.
CCI [REDACTED]			C																				CCI [REDACTED]
Itraconazole administration												X	X	X	X	X	X	X	X	X	X	X	Once daily with food (Section 5.3.1 and Section 6.1).
Tepotinib administration				X											X								Section 5.3.1. Section 6.1.
CCI [REDACTED]				X	X	X	X	X	X	X	X				X	X	X	X	X	X	X	Detailed PK sampling scheme in Table 1.	
Fecal sampling			X	X	X	X									X	X	X	X					All stools during the stay at CRU to be collected (Section 8.4).
Mild laxative					X											X							To be administered in the evenings (Section 8.4).

AE=adverse events, CRU=clinical research unit, ECG=electrocardiogram, FSH=follicle stimulating hormone, PK=pharmacokinetics, SARS-CoV-2=severe acute respiratory syndrome coronavirus type 2, TSH=thyroid stimulating hormone.

Table 1 **Tepotinib and Metabolite PK Sampling Schema**

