8.2.4 Clinical Safety Laboratory Assessments

- Blood and urine samples will be collected for the clinical laboratory tests listed in [Appendix 5](#) at the time points listed in the Schedule of Assessments (Section 1.3). All samples will be clearly identified.
- Additional tests may be performed at any time during the study, as determined necessary by the Investigator or required by local regulations.
- The tests will be performed by Nuvisan GmbH laboratory.
- The Investigator will review each laboratory report, document this review, and record any clinically significant changes occurring during the study as an AE, unless it does **not** meet the AE definition, as specified in [Appendix 4](#). The laboratory reports will be filed with the source documents.

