Appendix 5 Clinical Laboratory Tests

The protocol-required clinical laboratory assessments are in the following table:

Laboratory Assessments	Parameters				
Hematology	Platelet count		Mean corpuscular volume (MCV)	White Blood Cell Count with Differential: Neutrophils Lymphocytes Monocytes Eosinophils Basophils	
	Hemoglobin		Mean corpuscular hemoglobin (MCH)		
	Hematocrit				
Biochemistry	Blood Urea Nitrogen	Potassium	Aspartate aminotransferase	Bilirubin	
	Creatinine	Sodium	Alanine aminotransferase	Protein	
	Glucose	Calcium	Alkaline phosphatase	Albumin	
	Uric acid	Chloride	γ -Glutamyl transferase	Cholesterol	
		Inorganic phosphate	Lactate dehydrogenase	Triglycerides	
		Magnesium	Creatinine phosphokinase	Amylase	
				Lipase	
Routine Urinalysis	
 Specific gravity pH, glucose, protein, blood (hemoglobin), ketones, bilirubin, urobilinogen, nitrite, leukocyte esterase by dipstick Microscopic examination (if blood or protein is abnormal). Note: In case of a positive result for hemoglobin, leukocyte esterase, protein or nitrite, a urinary cell count will be performed				
Coagulation	
 INR aPTT 				
Other Screening Tests	
 FSH Serum hCG pregnancy test (as needed for a WOCBP) at all timepoints listed in the Schedule of Assessments (Section 1.3) Urine drug screen (to include at minimum: amphetamines, methamphetamines, barbiturates, ecstasy, cocaine, opiates, cannabinoids, benzodiazepines, methadone, phencyclidine, oxycodone, and tricyclic antidepressants, Screening and Day -1 / Day 11) Serology (human immunodeficiency virus I and II antibodies, hepatitis B surface antigen, hepatitis B core antibody, hepatitis C antibody) SARS-CoV-2 rapid antigen test at Screening, PCR test at admission on Day -1 Thyroid stimulating hormone Cotinine test (Screening and Day -1 / Day 11) Alcohol breath test (Screening and Day -1 / Day 11) Estimated Glomerular Filtration Rate based on Chronic Kidney Disease Epidemiology Collaboration Creatinine Equation (2009) All study-required laboratory assessments will be performed by a central laboratory (Nuvisan's clinical laboratory) 				

aPTT=activated partial thromboplastin time, FSH=follicle stimulating hormone, hCG=human chorionic gonadotropin, INR=International Normalized Ratio, PCR=polymerase chain reaction, SARS-CoV-2=severe acute respiratory syndrome coronavirus 2, WOCBP=woman of child-bearing potential.

CCI

Page 10

11

1000

1

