15.1 Adverse Events

All AEs recorded during the course of the study will be coded with the MedDRA, latest version at time of data base lock, and assigned to a SOC and a PT.

Treatment-emergent AEs (TEAEs) are those events with onset dates on or after the first administration of study intervention on Day 1. Any AE occurring before the administration of study intervention on Day 1 and resolved before administration of study intervention or not worsening after administration of study intervention on Day 1 will be included in the AE listings but will not be included in the summary tables (unless otherwise stated). These will be referred to as “pre-treatment” AEs. An AE occurring after administration of any study intervention will be counted towards the last intervention received before the onset, even if the event is not resolved at the beginning of the following intervention. An AE that worsens after a later intervention period will be counted towards both study interventions.

In case AE-related dates are partial, the available information will be used in a conservative approach to determine whether the AE is treatment-emergent.

All analyses described in Section 15.1 will be based on TEAEs if not otherwise specified. The AE listings will include all AEs (whether treatment-emergent or not). AEs outside the on-treatment period will be flagged in the listings.

Unless otherwise specified, TEAEs will be summarized, by number and percentage of participants with the TEAE in the category of interest, as well as the number of events, in total and by study intervention group, primary SOC and PT in alphabetical order for SOC and decreasing overall frequency for PT.

Each participant will be counted only once within each SOC or PT.

If an event was reported more than once due to change in intensity and change in relationship, the worst severity and the worst relationship to trial treatment will be tabulated.

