15.1.1 All Adverse Events

Number of treatment-emergent AEs and participants experiencing TEAEs will be summarized for Tepotinib, Itraconazole, Itraconazole+Tepotinib and overall, each in tables with:

- The number and percentage of participants with any TEAE, any related TEAE, any tepotinib-related TEAE, any itraconazole-related TEAE, any serious TEAE, any related serious TEAE, any tepotinib-related serious TEAE, any itraconazole-related serious TEAE, any severe TEAE, any related severe TEAE, any tepotinib-related severe TEAE, any itraconazole-related severe TEAE, any AEs of special interest (AESI), any TEAE leading to death, any related TEAE leading to death, any tepotinib-related TEAE leading to death, any itraconazole -related TEAE leading to death, any TEAE leading to study discontinuation
- The number and percentage of participants with at least one TEAE and the number of events by SOC and PT.
- The number and percentage of participants with TEAEs excluding SAEs and number of events, with frequency of participants $\geq 5\%$ in any study intervention arm by SOC and PT
- The number and percentage of participants with at least one TEAE and number of events by severity, SOC, and PT
- The number and percentage of participants with at least one related TEAE, tepotinib-related TEAE, itraconazole -related TEAE and number of events by SOC and PT
- The number and percentage of participants with at least one AESI recorded and number of events by SOC and PT.

Unless otherwise stated, AEs will be displayed with SOC terms sorted alphabetically and PTs within each SOC term sorted in descending overall frequency.

For determining incidence counts, within each level of TEAE term, if a participant experiences more than one occurrence, the participant will only be counted once for that TEAE.

Adverse events related to any study intervention are those events with relationship missing, unknown or yes.

In case a participant had events with missing and non-missing severity, the maximum non-missing severity will be displayed.

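### Do the by-intervention adverse event tables need changing because scheduled laboratory testing is denser after the combination dose than after tepotinib alone?

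*SAP*

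**What the plan says.** **Tables.** SAP 15.1.1 tabulates adverse events by intervention: "participants experiencing TEAEs will be summarized for Tepotinib, Itraconazole, Itraconazole+Tepotinib and overall". SAP 9 labels Day 1 as Tepotinib, Days 8-11 as Itraconazole and Days 12-18 as Itraconazole+Tepotinib. Its percentages for these tables use everyone who received the intervention in question.

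**Attribution.** SAP 15.1: "An AE occurring after administration of any study intervention will be counted towards the last intervention received before the onset".

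**Laboratory findings.** Protocol 8.2.4 tells the investigator to "record any clinically significant changes occurring during the study as an AE", and allows extra tests whenever they are judged necessary.

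**Schedule (Protocol 1.3).** The row "Clinical laboratory tests (blood and urine" is marked at Screening, Day -1, Day 10, Days 12 to 15 and once late. The row "Vital signs & safety ECG" is marked at Screening and on Days -1, 1, 2, 11, 12, 13, 14 and 15, and once late, with dosing-day measurements taken predose. The row "AE/concomitant medication review" is marked in every column.

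**Purpose.** Protocol 9.1 limits the analysis to description. The safety objective (Protocol 3, SAP 5) concerns tepotinib given with itraconazole.

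**The concern.** The columns look comparable because they contain the same people and use the same kind of denominator, but the chance of finding a laboratory abnormality differs between them. Protocol 2.3.1 lists creatinine, amylase and lipase, ALT and AST, and ALP increases among the tepotinib risks, and describes creatinine rises after single doses as transient. A rise that resolved before Day 10 would escape the scheduled tests after the first dose, while the same rise after the second dose could be caught on Days 13 to 15.

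A reader could then see laboratory events under the combination and none under tepotinib alone, and read this as an interaction effect on safety even if itraconazole added nothing. Neither SAP 15.1.1 nor SAP 15.3 comments on the unequal testing.

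**Working it through.** The plan gives no figure on this point, so there is none to reproduce.

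**1. Is the schedule row read correctly?** Some rows in the same part of the table can be checked against text. The residence row agrees with the Synopsis ("residence in the Clinical Research Unit from Days -1 to 4 and Days 11 to 15"), and the cotinine row agrees with Appendix 5 ("Cotinine test (Screening and Day -1 / Day 11"). Other marks are damaged in the text copy:
- The ambulatory row lacks Day 10, although the Synopsis gives Days 5 to 10.
- The last laboratory mark falls in the Day 19 cell, although Protocol 4.4 puts the follow-up assessments on Day 20.
- In the second part of the table, the itraconazole row sits two columns late and the tepotinib row one column late.

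Moving the Day 10 laboratory mark by one column (to Day 9 or 11) leaves zero tests under tepotinib alone. A lost mark, or a two-column shift to a predose sample on Day 8, would make it one. The imbalance survives either way; the exact zero is less certain.

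**2. Scheduled post-dose assessments per column**, using the SAP 9 labels and the SAP 15.1 attribution rule:

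| | Tepotinib | Itraconazole | Itraconazole+Tepotinib |
|---|---|---|---|
| Laboratory | 0 | 1 (Day 10), or 2 if the Day 12 draw is predose | 4 (Days 13, 14, 15 and the late visit), or 5 if the Day 12 draw is postdose |
| ECG and vital signs | 1 (Day 2) | 2 (Day 11, Day 12 predose) | 4 (Days 13, 14, 15 and the late visit) |
| Window | Day 1 to 8: 7 days | Day 8 to 12: 4 days | Day 12 to 20: 8 days |
| Itraconazole doses | 0 | 4 | 7 |

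**3. Illustrative size.** Assume an equal risk q per tepotinib dose of a laboratory change that would be recorded as an adverse event if measured, with full detection under the combination. P(at least one) = 1 - (1 - q)^N.
- q = 2%: 1 - 0.98^14 = 0.246; 1 - 0.98^18 = 0.305.
- q = 5%: 1 - 0.95^14 = 0.512; 1 - 0.95^18 = 0.603.

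Expected numbers are Nq = 0.28 to 0.90 participants. If only half are detected, q is replaced by 0.5q and the chance is 13% to 37%.

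If unscheduled tests found 20% of cases under tepotinib alone, the chance of at least one under the combination and none under tepotinib alone is the figure above times (1 - 0.2q)^N, treating the two periods as independent:
- Smallest: 0.246 × 0.996^14 = 0.233.
- Largest: 0.603 × 0.99^18 = 0.503.

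With half detection the range is 12% to 31%.

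A different model, with risk p = 1% to 5% per test and k tests, gives 1 - (1 - p)^(kN): from 43% (p = 1%, k = 4, N = 14) to 99% (p = 5%, k = 5, N = 18). The answer follows the assumed rate, so these figures show that the effect is possible, not how large it is in this trial.

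**4. Would a change to the tables help?**
- *A row leaving out events found only by a scheduled test.* Daily adverse event review makes questioning even, but the columns still differ in window length (7, 4 and 8 days) and in itraconazole exposure (0, 4 and 7 doses). The row would therefore not be comparable across columns. It would also need a judgement for each event on how it was found, in an open-label study and with no data field described for it. Asymptomatic liver findings that meet the definition of the only event of special interest (Protocol 8.3.7, SAP 15.2.3) would be left out.
- *A footnote giving the number of tests per column.* This is harmless, but it changes no count and no planned conclusion.

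**The case for a change.** The strongest case for a change is that someone reading only the adverse event table cannot see the testing schedule. SAP 4 says results may go into regulatory submissions or manuscripts. Events of special interest are also tabulated by intervention, so a liver finding under the combination alone could be taken for an interaction effect. A row and a footnote cost little with at most 18 participants, and events could be classified at the data review meeting already planned before database lock.

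The mechanism stands, and so does the unequal testing, even if one mark was lost. The argument for the consequences is weaker:
- Only changes judged clinically significant become adverse events. A transient creatinine rise, which Protocol 2.3.1 attributes to competition for tubular secretion, need not qualify.
- Protocol 2.3.1 describes ALP increases as low grade and nonserious, and reports no clinically relevant hypoalbuminemia after single doses.
- SAP 15.3 summarises hematology and biochemistry by intervention and time point with change from baseline, and lists abnormal results. The missing visits can be seen there.
- SAP 15.1 lists every adverse event, and SAP 9.3 computes time from dosing for treatment-emergent events, so the timing of any laboratory event can be traced.

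The low cost of a new row does not offset its subjectivity or its lack of comparability.

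**Conclusion.** No change to the plan is needed. Laboratory-detected adverse events are not found with equal chance in each column: as the schedule reads, there are 0 scheduled post-dose tests under tepotinib alone, 1-2 under itraconazole and 4-5 under the combination. The zero should be confirmed on the published page.

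The effect is confined to an informal reading across descriptive columns. The stated objective is served by the combination period, which has the most tests, and neither document plans a safety comparison with tepotinib alone. The extra row is a poor trade-off and the footnote brings no gain in any conclusion. An author of the study report who knows the schedule would not draw a contrast from laboratory-derived events between these two columns.

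The 25% to 60% illustration rests on an assumed 2% to 5% risk and full detection, neither of which comes from the documents. The conclusion does not depend on it.

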15.1.2 Adverse Events Leading to Discontinuation of Study Intervention

A listing of TEAEs leading to discontinuation of study intervention, or discontinuation of study, if any, will be provided.

The frequency (number and percentage) of participants with TEAEs leading to permanent discontinuation of each study intervention by study intervention will also be provided in a table.

15.2 Deaths, Other Serious Adverse Events, and Other Significant Adverse Events

15.2.1 Deaths

A listing of deaths, if any, will be provided.

15.2.2 Serious Adverse Events

A listing of serious AEs (SAEs), if any, will be provided.

Summary table of the number and percentage of participants with at least one SAE by SOC and PT will also be provided.

15.2.3 Other Significant Adverse Events

The following AESI were defined:

- AEs suggestive of drug-induced liver injury including hepatic/liver failure and hepatitis (noninfectious) are considered AESIs.

More information can be found in the CSP, section 8.3.7.

AESI will be identified in the AE listings. Summary table of the number and percentage of participants with at least one AESI by SOC and PT will also be provided.

15.3 Clinical Laboratory Evaluation

Listings and summary statistics at each assessment time will be presented using the Système International (SI) units. Normal ranges will be provided by the central laboratory, and out of range flags will be calculated based on the normal ranges. Laboratory data not transferred from the central laboratory in SI units will be converted to SI units before processing. Both original units and SI units will be provided in the SDTM domain.

Safety laboratory parameters are separated into:

- Hematology (including coagulation)
- Biochemistry
- Urinalysis
- Other tests

Hematology and biochemistry will be summarized by study intervention and time point using descriptive statistics for baseline (see definition in Section 9), each evaluation during the study, and change from baseline to each evaluation.

Summaries will include all assessments from screening on.

Listings of abnormal test results (low and high) will also be provided.

15.4 Vital Signs

Vital signs data will be summarized by study intervention and time point using descriptive statistics for baseline (see definition in Section 9), each evaluation during the study, and change from baseline to each evaluation. Listing of vital signs data will be provided.

Vital sign summaries will include all vital sign assessments from screening on. All vital sign assessments will be listed, and those collected outside the on-treatment period will be flagged in the listing.

15.5 Other Safety or Tolerability Evaluations

Safety ECG data will be summarized by study intervention and time point using descriptive statistics for baseline (see definition in Section 9), each evaluation during the study, and change from baseline to each evaluation. Listing of safety ECG data will be provided.

ECG summaries will include all ECG assessments from screening on. All ECG assessments will be listed.

The analysis of QT data is complicated by the fact that the QT interval is highly correlated with heart rate. Because of this correlation, formulas are routinely used to obtain a corrected value, denoted QTc, which is independent of heart rate. This QTc interval is intended to represent the QT interval at a standardized heart rate. Several correction formulas have been proposed in the literature. The QT interval will be corrected for heart rate by the Fridericia's formula, QTcF, is defined as

$$QTcF = \frac{QT}{\sqrt[3]{RR}} ,$$

where RR represents the RR interval of the ECG, in seconds, and can be estimated as 60/Heart Rate.

Investigator reported interpretation results will also be tabulated by study intervention and time point using the number and percentage of participants for each interpretation category (Normal, Abnormal Not Clinically Significant [NCS], Abnormal Clinically Significant [CS]).

16 Analyses of Other Endpoints/Estimands

